#### **8.4.9 Safety biomarkers**

The endocrine (pituitary) function, gonadal function, growth and development, and bone development function of each patient will be evaluated using the safety biomarker tests described in the [Table 8-5](#).

Samples will be collected at the time points defined in the Assessment Schedule ([Table 8-2](#)).

A central laboratory will be used for analysis of all safety biomarker specimens. Details on the collection, shipment of samples and reporting of results by the central laboratory are provided to investigators in the central laboratory manual.

**Table 8-5 Safety biomarker assessments**

| Test Category                  | Test Name   |
|--------------------------------|---|
| Endocrine (Pituitary) function | 

• TSH (and free Thyroxine (fT4) if TSH is abnormal)

• Luteinizing hormone (LH)

• Follicle-stimulating hormone (FSH)

 |
| Gonadal function               | 

• Inhibin B in men

• Estradiol in women

• Testosterone in men

   |
| Growth and development         | 

• IGF-1

   |
| Bone development               | 

• BALP

• N-terminal or C-terminal cross-linked telopeptide of type I collagen (NTX or CTX)

                                  |

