### Amendment rationale

The primary purpose of Amendment 03 is to align the protocol with the amended FDA Written Request and PDCO positive opinion on the request for modification of the agreed PIP for Lutathera issued on 28-Jun-2023 and 13-Oct-2023 respectively. On 01-Dec-2023, the final EMA Decision/Acceptance for the modification of the agreed pediatric investigation plan for Lutathera (EMEA-002950-PIP01-20-M01) was received. It was agreed with both Health Authorities that the primary analysis of organ dosimetry, pharmacokinetic (PK) and safety data will be carried out across adolescent patients with GEP-NETs and PPGLs, as these parameters are not expected to vary substantially depending on tumor type. The main risks arising from treatment with Lutathera are radiation toxicities affecting either kidney function or bone marrow, which applies to both GEP-NET and PPGL. Biodistribution to organs and normal tissues and thus organ dosimetry and safety is not anticipated to be affected by the disease. Therefore, the data from both GEP-NET and PPGL patients can support the overall comparison between adolescents and adult GEP-NET patients during the primary analysis.

Based on the above rationale, the study design, study objectives and endpoints are modified as follows:

- The total number of patients required for the primary analysis remains the same, with at least 8 adolescent patients evaluable for the primary endpoints, but the primary analysis will be pooled across indications. Consequently, this change leads to an updated sample size from 8 GEP-NET patients to 8 adolescent patients across indications including a minimum of 3 adolescents with GEP-NET. With the enrolled number of patients, the updated recruitment target has already been met.
- The co-primary and secondary objectives will be evaluated in GEP-NETs and PPGLs as a pooled cohort instead of GEP-NETs cohort alone, serving the same purpose to compare adolescent data with data from adult GEP-NET patients.

In addition, the protocol amendment included the following changes:

- Laboratory assessments on safety biomarkers of endocrine and gonadal function were added to long-term follow up visits. This implements FDA written request requirements that safety follow up should include monitoring for pituitary dysfunction given the potential risk for toxicity to the pituitary gland.

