For the patients enrolled in the PPGL cohort, a monitoring for development of hormonal crisis symptoms due to potential tumor lysis and excessive catecholamine release (such as hypertension, pallor, sweating, palpitations) (see [Section 1.1](#)) will be performed after each Lutathera dose. A combined  $\alpha$ - and  $\beta$ -adrenergic blockade is a standard treatment for PPGL patients with pheochromocytoma in order to control blood pressure ([Neumann 2019](#)), and any additional medications will be administered in this study by investigator if necessary per the medical judgment and local standards. In a study of 20 adult PPGL patients treated with  $^{177}\text{Lu}$ -dotatate PRRT, hypertension flare was observed in only one patient, who had inadequate alpha- and beta-blockade before treatment resulting from patient nonadherence to prescribed therapy ([Kong 2017](#)). An appropriate adrenergic blockade, safety monitoring and patient control will be carried out in all adolescents with PPGL enrolled in the NETTER-P study.

Considering the age of participants, additional potential safety concerns in the pediatric population will be controlled via assessment of safety biomarkers. This includes potential effects of treatment with Lutathera on endocrine (hypothalamic-pituitary) function, gonadal function, growth and bone development that will be controlled during and after the treatment with Lutathera ([Section 8.4.9](#)).

All safety effects of Lutathera will be carefully assessed in this study, and patients will be closely monitored.

As this is the first study of Lutathera in adolescents with GEP-NETs and PPGLs, its efficacy and safety has not been established in this population yet. However, based on adult efficacy and similarities between adolescents and adults, it is expected that Lutathera administered in the study may bring therapeutic benefit to adolescents with GEP-NETs and PPGLs. This study will be essential to bring new potential therapeutic options for adolescent GEP-NET and PPGL patients.

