**Nephrotoxicity:** Since Lutathera is cleared through the kidneys and reabsorbed by the kidneys, the kidneys have always been considered the “critical organs”. An infusion of amino acid is used for kidneys protection by inhibition of tubular reabsorption of Lutathera. Pursuant to these risk minimization efforts and in addition to the criteria of dose-modifying toxicities and criteria of inclusion (at baseline and before subsequent treatments) pertinent to renal function measurements, renal and urinary tract toxicities are considered AESI. Investigators must report as AESI renal toxicities including renal failure (ranging from significantly reduced measured or estimated creatinine clearance to clinically overt renal failure other than that of obvious non-IMP-induced origin), suspected radiation nephropathy of any type, such as radiation-induced thrombotic microangiopathy (manifested with, e.g., proteinuria, hypertension, edema, anaemia, decrease serum haptoglobin), or general symptoms and signs of acute radiation toxicity (e.g., increased frequency and urgency of urination, nocturia, dysuria, bladder spasm, bladder obstruction, genitourinary ulceration or necrosis).

**Endocrine (hypothalamic-pituitary and growth) disorders:** Since the potential effect of the Lutathera treatment on the pituitary-gonadal and pituitary-thyroid axes is not well described in the adolescent population, the endocrine effects will be closely monitored via specific biomarkers. Any suspected endocrine toxicity should be considered AESI regardless of severity.

**Effects on bone development:** Radiation exposure has a potential effect on the overall quantity and quality of bone by interfering with the trabecular architecture through increased osteoclast activity and decreased osteoblast activity. Biomarkers of bone metabolism help to detect the metabolic imbalance and identify bone toxicities. Any suspected bone toxicity should be considered AESI regardless of severity.

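### Free T4 is measured only when TSH is abnormal, so the laboratory panel could show a normal thyroid result in a patient with pituitary-thyroid toxicity whose TSH stays in range

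*Protocol*

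**What the plan says.** Protocol Section 8.4.9 gives the biomarker panel its task: "The endocrine (pituitary) function, gonadal function, growth and development, and bone development function of each patient will be evaluated using the safety biomarker tests" listed in Table 8-5. Under "Endocrine (Pituitary) function" that table has LH and FSH without condition, and the thyroid entry "TSH (and free Thyroxine (fT4) if TSH is abnormal" (closing bracket omitted). Estradiol in females, testosterone and inhibin B in males, and IGF-1 are also unconditional.

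Three other places say what the panel is looking for:

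- Section 4.5 gives the concern as "potential effects of treatment with Lutathera on endocrine (hypothalamic-pituitary) function".
- Section 10.1.5, on endocrine events of special interest, says that the "potential effect of the Lutathera treatment on the pituitary-gonadal and pituitary-thyroid axes is not well described in the adolescent population" and that "the endocrine effects will be closely monitored via specific biomarkers".
- The Amendment 03 rationale extends the endocrine and gonadal biomarkers to long-term follow-up, because the regulator asked that "safety follow up should include monitoring for pituitary dysfunction given the potential risk for toxicity to the pituitary gland".

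SAP 2.6.4 summarises safety biomarkers by parameter, as worst value and as shift from baseline to worst value. It covers the on-treatment period and then repeats the summaries with short-term and long-term follow-up included. The SAP does not mention free T4.

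**The concern.** Letting TSH decide whether free T4 is measured suits disease of the thyroid gland, where a healthy pituitary raises TSH as thyroid hormone falls. The hazard named here is to the pituitary. A damaged pituitary may be unable to raise TSH, so low free T4 can sit beside a TSH within the reference range. In that patient the trigger does not fire and the informative test is not done.

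Laboratory abnormalities during long-term follow-up are a secondary endpoint, and any suspected endocrine toxicity is an event of special interest whatever its grade. A patient affected in this way would enter the TSH tables as normal and would be missing from any free T4 table. The study report could then say less about the pituitary-thyroid axis than its tables appear to.

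**Working it through.** The plan states no figure on this point, so the check sets its passages side by side.

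1. **Purpose.** Sections 4.5 and 10.1.5 and the Amendment 03 rationale all place the hazard at hypothalamic-pituitary level. Section 10.1.5 names the pituitary-thyroid axis.

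2. **Tool.** The only test of that axis performed at every biomarker time point is TSH. No unconditional free T4 appears in the chemistry panel (Table 8-4), in the readable rows of the assessment schedule (Table 8-2) or in the SAP.

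3. **Logic of the trigger.** There are three cases:
   - Primary thyroid failure: TSH moves out of range, free T4 is measured, and the case is seen.
   - Central failure with TSH out of range: free T4 is measured, and the case is seen.
   - Central failure with TSH in range: free T4 is not measured, and the thyroid result reads normal.

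   The third case belongs to the hazard the panel is meant to monitor. That it can occur is basic feedback physiology. Neither document discusses it or says how often it happens.

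4. **Comparison within Table 8-5.** On the gonadal axis the pituitary hormones (LH, FSH) and the end-organ hormones (estradiol or testosterone) are measured together without condition. The thyroid pair is conditional, and no reason is given.

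5. **Effect on the analysis.** SAP 2.1.1 takes baseline as the last value on or before first administration. Under the reflex rule, free T4 is absent by design when TSH is in range, and in most patients that would include baseline. Protocol Section 12 does not replace missing data. Any free T4 shift table would therefore mostly lack baselines and would contain only patients selected on TSH.

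6. **Size of the change.** From the readable part of Table 8-2 and its footnotes 13 to 15:
   - Cycle 1 Day 1 pre-dose; Cycle 1 Week 7 or Cycle 2 pre-dose; Cycle 4 Week 7 or end of treatment: 3 time points.
   - Long-term follow-up every 6 months from month 12 to month 60 after the last dose: (60 − 12)/6 + 1 = 9 time points.
   - Total 3 + 9 = 12 per patient. For the 11 patients enrolled by 14-Dec-2023, 12 × 11 = 132 assays over the full schedule.

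   The count is approximate. The columns of Table 8-2 are broken in the available text, Table 8-1 also lists Cycle 3 and short-term follow-up for these biomarkers, and enrolment has a minimum but no cap. For patients already treated, only the remaining time points count.

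**The case against.** The strongest reply is that the documents contain no contradiction in figures. They show a conditional test, and the step from an in-range TSH to a missed case is outside physiology with no frequency attached. Several safeguards also exist. Section 8.4.6 requires further specimens on clinical or laboratory evidence of toxicity. Section 10.1.1 has adverse events sought at every visit. Section 10.1.5 makes mere suspicion of endocrine toxicity reportable. Height and weight are followed every six months in long-term follow-up. Table 8-5 does not define an abnormal TSH, and Section 10.1.1 allows a marked change from baseline to count when laboratory values are judged clinically significant, so a falling but in-range TSH might qualify. The central laboratory manual, which may define the trigger, is not available.

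Much of this stands, and it limits the point. The safeguards depend on symptoms, on clinical suspicion or on some other abnormality, so they narrow the gap without closing it. During follow-up, endocrine events of special interest are recorded only if judged related to treatment (Section 8.4.1), so mild or non-specific symptoms may not be captured.

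Four stronger readings are tempting, and the documents do not support them:

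- *An affected patient has a normal panel at every visit for five years.* That would need isolated thyroid-axis damage and an in-range TSH every time. LH, FSH, sex steroids and IGF-1 are always measured and may reveal wider injury.
- *The thyroid is the one axis without its end-hormone.* Table 8-5 has no adrenal-axis test at all.
- *The detection rate is one minus the share of in-range TSH results.* The share is unknown. The bound holds only if it refers to patients whose TSH never leaves range, since one out-of-range result among repeated tests triggers free T4.
- *The extra assays number at most 132.* With enrolment uncapped and the schedule only partly readable, that is an estimate and not a ceiling.

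**Conclusion.** The point holds in limited form. The panel is there to look for pituitary toxicity, including on the pituitary-thyroid axis, yet free T4 is withheld when TSH is in range. Central hypothyroidism with an in-range TSH could therefore pass as a normal thyroid result unless clinical suspicion or another abnormality prompts extra testing. The rule still finds primary thyroid failure and central cases with an out-of-range TSH.

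This rests on one premise from outside the documents, that a damaged pituitary can leave TSH in range while free T4 is low, and on reading abnormal as outside the reference range. No frequency is given, so no detection rate or number of missed cases should be stated. The primary endpoints of absorbed dose and first-cycle safety do not hinge on it. What is affected is how far the long-term endocrine safety results can be interpreted. It is a recommended change.

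**What to change.** In Protocol Table 8-5, replace the conditional entry with TSH and free T4, both measured at each remaining safety-biomarker time point. Use the existing central-laboratory sample where volume allows. The documents do not give the sample type or volume, and Section 4.5.1 commits to keeping blood volume low, so this should be confirmed with the laboratory.

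In SAP 2.6.4, name free T4 beside TSH in the biomarker summaries. Report the worst value as low, normal or high for all patients with a measurement. Report shift from baseline only where a baseline free T4 exists, with the number of such patients shown, because patients dosed before the change may have none.

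No visit is added and no treatment rule changes. The cost is about 12 assays per patient over a full schedule (roughly 130 for the 11 patients enrolled by 14-Dec-2023, fewer once elapsed time points are removed), possibly a little more blood, and a few incidental mild free T4 deviations to follow up.

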#### **8.4.10 Performance score assessment**

Karnofsky performance score (KPS) evaluation must be completed by a medical professional at the time points defined in the Assessment Schedule (Table 8-2). If applicable and preferred by Investigator, KPS can be replaced by Lansky Play-Performance Scale assessment.

#### **8.4.11 Tumor response assessment**

CT/MRI imaging will be done at screening

### **9 Study discontinuation and completion**

#### **9.1 Discontinuation and completion**

##### **9.1.1 Study treatment discontinuation and study discontinuation**

Discontinuation of study treatment for a participant occurs when study treatment is stopped earlier than the protocol planned duration and can be initiated by either the participant or the investigator.

The investigator must discontinue study treatment for a given participant if, he/she believes that continuation would negatively impact the participant's well-being.

Study treatment must be discontinued under the following circumstances:

- Participant/guardian decision
- Pregnancy
- Any situation in which study participation might result in a safety risk to the participant including unacceptable adverse event.

If discontinuation of study treatment occurs, the investigator should make a reasonable effort to understand the primary reason for the participant's premature discontinuation of study treatment and record this information.

Participants who discontinue study treatment or who decide they do not wish to participate in the study further should NOT be considered withdrawn from the study UNLESS they withdraw their consent (see [Section 9.1.2 'Withdrawal of Informed Consent' section](#)).

**Where possible, all patients who discontinue study treatment should return for the EoT/Early Termination Visit assessments, and continue into the full Follow-up period as indicated** in the Assessment Schedule. If they fail to return for these assessments for unknown reasons, every effort (e.g. telephone, e-mail, letter) should be made to contact the participant/pre-designated contact as specified for lost to follow-up ([Section 9.1.3](#)). This contact should preferably be done according to the study visit schedule.

If the participant cannot or is unwilling to attend any visit(s), the site staff should maintain regular telephone contact with the participant, or with a person pre-designated by the participant. This telephone contact should preferably be done according to the study visit schedule.

After study treatment discontinuation, if the patient is unwilling to perform all scheduled assessments, then at a minimum, in abbreviated visits, the following data should be collected at clinic visits or via telephone/email contact:

- Survival status
- New / concomitant treatments, including all antineoplastic therapies
- Adverse Events / Serious Adverse Events

During the COVID-19 pandemic, for patients who are unable to come to the study site for their scheduled visit, conducting patient study visits on schedule through phone calls and virtual contacts (e.g. teleconsult) may be possible. As patient safety is the number one concern, patients may need to discontinue treatment based on the investigator's clinical judgment or patient's own decision. The investigator should document in the source notes as clearly as possible the decisions made around continuing or discontinuing study treatment for a patient and the risk-benefit for each case as it may arise. The investigator should consider if alternative therapeutic options exist and may be warranted based on the individual benefit-risk for the patient.

In extraordinary situations due to the very short half-life of radionuclides, e.g. a sudden temporary supply disruption and/or a quality finding after release of the product, the investigator may immediately be:

1. advised on how to manage participants in screening or on treatment;
2. informed to withhold doses from impacted batch and not administer them to the participant;

and/or

3. asked to closely monitor participants who have received a dose from an impacted batch for adverse events.

### **9.1.1.1 Replacement policy**

In general, no treated patients will be replaced, and all patients who received at least one Lutathera dose will be used for the primary safety analysis. However, more than 8 patients may be enrolled if deemed necessary, e.g. in case that a patient is not evaluable for the primary dosimetry analysis.

### **9.1.2 Withdrawal of informed consent**

Withdrawal of consent/opposition to use of data and/or biological samples occurs in countries where the legal justification to collect and process the data is consent and when a participant:

- Explicitly requests to stop use of his/her data

and

- No longer wishes to receive study treatment

and

- Does not want any further visits or assessments (including further study-related contacts).

This request should be as per local regulations (e.g. in writing) and recorded in the source documentation.

Withdrawal of consent impacts ability to further contact the participant, collect follow-up data (e.g. to respond to data queries) and potentially other country-specific restrictions. It is therefore very important to ensure accurate recording of withdrawal vs. discontinuation based on the protocol definitions of these terms.

In this situation, the investigator should make a reasonable effort (e.g. telephone, e-mail, letter) to understand the primary reason for the participant's decision to withdraw his/her consent/exercise data privacy rights and record this information. The Investigator should clearly document if the participant has withdrawn his/her consent for the use of data in addition to a study discontinuation.

Study treatment must be discontinued and no further assessments conducted, and the data that would have been collected at subsequent visits will be considered missing.

Further attempts to contact the participant for the study purpose are not allowed unless safety findings require communicating or follow-up.

If the participant agrees, a final evaluation at the time of the participant's withdrawal of consent/exercise data privacy rights should be made as detailed in the assessment table.

Further details on withdrawal of consent or the exercise of participants' data privacy rights are included in the corresponding consent form.

### **9.1.3 Lost to follow-up**

For participants whose status is unclear because they fail to appear for study visits without stating an intention to discontinue or withdraw consent (or exercise other participants' data privacy rights), the Investigator must show "due diligence" by documenting in the source documents steps taken to contact the participant, e.g. dates of telephone calls, registered letters, etc. A participant should not be considered as lost to follow-up until due diligence has been completed or until the end of the study.

#### **9.1.4 Early study termination by the sponsor**

The study can be terminated by the Sponsor at any time.

Reasons for early termination:

- Unexpected, significant, or unacceptable safety risk to participants enrolled in the study
- Decision based on recommendations from DSMB after review of safety data
- Practical reasons (including slow enrollment)
- Discontinuation of study drug development

In taking the decision to terminate, Sponsor will always consider participant welfare and safety. Should early termination be necessary, participants must be seen as soon as possible and treated as a prematurely withdrawn participant. The investigator may be informed of additional procedures to be followed in order to ensure that adequate consideration is given to the protection of the participant's interests. The investigator or sponsor depending on local regulation will be responsible for informing IRBs/IECs of the early termination of the trial.

